## **A. Type of Research**

The studies involves behavioral research. Our goal is to digitize and automate a number of scientifically validated processes to ensure that suicidal patients in the emergency department receive them. The focus of the studies is to compare the effects of Jaspr versus CAU with suicidal patients in the ED as well as JAH versus CAU with outpatients experiencing suicidality, with the former having particular interest in suicidality, ED/hospital admissions, self-efficacy, and treatment satisfaction.

## **B. Purpose/Objective of the Study**

The overall purpose of the ED study is to evaluate the app we recently developed, called Jaspr, that can be used on a tablet and/or smartphone by suicidal patients in the ED and their care providers. Jaspr also includes a companion mobile app patients may use after discharge on their smartphone. Jaspr is designed to reduce unnecessary hospitalization, length of stay in the ED, and ED/hospital readmissions while also improving patient satisfaction and providing support to

ED providers (e.g., nurses, social workers, physicians). The overall purpose of the Telehealth study is to evaluate the effectiveness of the companion mobile app, called Jaspr-at-Home, that can be used by outpatients experiencing suicidality, when implemented in a telehealth context.

## C. Background of the Study

In our Phase I preliminary research for this project, we developed and tested the feasibility of a Jaspr prototype (called Virtual CAMS) for “proof of concept”. The prototype, for use with suicidal ED patients and medical providers was based on a nurse avatar (“Louise”) that reduced readmissions through enhanced medical discharge planning, included “[name]” (based on CAMS treatment developer, [name]) to administer a CAMS-oriented Suicide Status Interview (SSI; based on the Suicide Status Form, SSF) and a clinical decision-making support tool for providers that summarizes the patient’s suicide risk based on the SSI.

Proof of concept was determined in two stages: (1) a formative evaluation during the iterative development of Jaspr where feedback was obtained from target end-users, and (2) a summative evaluation consisting of a feasibility test (usability, acceptability, satisfaction) of “[name]” with suicidal ED patients. During this preliminary study, we visited Mayo Clinic, HealthPartners’ and four Allina Health EDs to understand their workflow and discuss with administrators to understand their challenges treating suicidal ED patients. We met with over 25 Allina administrators and ED directors to discuss how innovative technologies like Jaspr might improve ED services. We developed and tested all Jaspr elements proposed for Phase I: (1) a tablet-based avatar (“[name]”) performing a 15-minute segment of the CAMS SSI; (2) the discharge disposition clinical decision support tool that distills Jaspr SSI content into an easy-to-review provider report (content and graphics only); and (3) “Caring Contacts” post-discharge messages. We also developed two videos of peer specialists with lived experience with suicide (generating hope) and videos of [name] introducing patients to the SSI for later testing of whether suicidal ED patients preferred videos to an avatar.

In Phase II preliminary research, we conducted extensive research and analysis of competitor apps to analyze market competition and gathered ideas about designs and content to include in Jaspr. Design summit meetings were held to further refine the initial design of the app. In collaboration with systems stakeholders, various personas were created to better understand the workflow in the ED. Personas for different patient journeys in the ED were created, as well as personas for loved ones accompanying the patient, business development leaders, masters-level assessors, ED physicians, and stakeholders. Patient personas were informed by interviews with 15 people with lived experience (PLE) who previously sought ED services during their suicide crises. During this phase, user-centered research was conducted to obtain feedback about Jaspr’s patient-facing features. Patients in the ED and inpatient unit were interviewed at Harborview Medical Center, Mayo Clinic, and Allina Health. With consultation from suicide experts, we received validation and enhanced understanding to develop Caring Contacts content for the app. We also created 3.5 hours of video content of PLEs discussing various topics including relationship to suicide now, experience in the ED, skills to stay well and manage difficult emotions, personal stories, first day/week out of hospital, and “my wish for you”. These video clips were culled and tested within the NowMattersNow.org collection of behavioral skills to include in Jaspr-at-Home a companion mobile app patients may use on their own smartphone after discharge.

**Preliminary Findings:** Four important findings emerged through our initial Phase I, 80+ hours of testing and interviews. First, administrators and providers universally viewed tablets as acceptable technology to deliver Jaspr as patients are always under observation – either directly monitored in open-spaces or with cameras when in a closed room. Second, they excluded only psychotic and/or severely agitated patients as inappropriate to use Jaspr. Third, all participants liked the hope-instilling videos by consumer/peer specialists and viewed them as a nice counterbalance to the “[name]” SSI. Finally, patient participants preferred a simple avatar (like “Nurse Louise”) using a computer-generated voice instead of video delivery of CAMS or use of [name] actual voice for “[name].” Stated plainly by one participant, “It’s clear that the avatar is a computer and not a person trying to get into my head.” While not all suicidal

patients felt strongly in their preference, all found the simple avatar acceptable and valuable to use.

Preliminary study results from the Phase II user-centered research are similarly positive, with 95% of participants endorsing that they would save the content they encountered for use after leaving the ED, 100% identified the features as “helpful”, and 100% indicated they would like to see the app available for use in EDs for suicidal individuals.

## 4. Participant Selection

### A. Inclusion and Exclusion Criteria

All participants must be 18 years or older and English-speaking (Jaspr is currently only available in English. A Spanish version will be developed after the English version of Jaspr is successfully commercialized).

#### ***Patient Participants:***

ED Study Inclusion Criteria: Patient participants must: 1) currently be in the ED seeking treatment for suicidal behavior; 2) be medically and clinically stable as deemed by ED medical personnel or other treatment provider on patient’s care team; 3) have access to a computer or other device (smartphone, tablet) with Internet connection; 4) have access and regularly use an Apple or Android smartphone; 5) have a stable address and housing for the last 30 days.

Telehealth Study Patient Inclusion Criteria: 1) Currently receiving outpatient treatment services for suicidality; 2) have access to a computer or other device (smartphone, tablet) with Internet connection; 3) currently has and regularly uses an Apple or Android smartphone; 4) has a stable address and housing.

Patient Exclusion Criteria: Patients who are 1) acutely psychotic, severely agitated; patients with significant intoxication or other impairment that may interfere with providing consent and meaningful feedback (as determined by their medical provider); 2) have no access or way to access phone or computer (or other device) with Internet connection; and 3) homeless or have unstable housing in the past 30 days will be excluded from the study.

Additional Exclusion Criterion (Telehealth Study only): Prior use of Jaspr/Jaspr-at-Home.

#### ***Provider Participants (ED study only):***

Inclusion Criteria: Providers must be currently serving in the ED as a medical provider who treats patients with suicidal behaviors. There are no exclusion criteria.

### B. Gender

The research team will maintain a focused effort on ensuring that the percent of women participants recruited for this study are representative of the broader group of target end-users. Women as well as men will be eligible for participation in this study. Because of the overrepresentation of men who present to emergency departments as suicidal, it is expected men will represent approximately 60% of our sample population. Pregnant women will not be excluded from this study and method of birth control will not be measured as this research will impose no risk to the fetus.

### C. Racial/Ethnic Origin

Our goal is to achieve a minimum of 25% involvement by ethnic and racial minority participants among patient and provider participants. [name] has successfully employed a number of approaches in her previous research to reach recruitment targets, in particular with respect to ethnic and racial minorities. If needed, we will pursue these approaches

including: Significantly expanding recruitment efforts in ethnically and racially diverse geographic locations, and to agencies serving ethnic and racial minorities, and taking a much more active, personal approach throughout the recruitment effort. This latter approach often involves identifying what matters to the organization in advance and seeking ways to link our request to their needs/interests/mission. This approach may involve visiting (either virtually or directly) the hospital and may involve providing an in-service, as requested by the director. We can easily provide these services through our online community format.

Should we continue to encounter difficulty meeting our targets for recruitment of ethnic and racial minority participants after applying these methods, we will form an ethnic and racial minority recruitment advisory committee, chaired by [name], an expert on cross-cultural clinical research and a close colleague of [name]. The task force will then examine recruitment efforts to date in an effort to identify potential problems or barriers to access that may account for the continued low enrollment. Solutions will then be generated, implemented, and reevaluated. We will seek input from this advisory board as needed to ensure we have fulfilled our stated aims described here.

#### **D. Vulnerable Populations**

The risk to participants in this research is minimal when applying NIMH risk standards and designations. According to these NIMH guidelines, “minimal risk to subjects means that the probability and magnitude of harm or discomfort anticipated in the research are not greater than those ordinarily encountered in daily life or during the performance of routine physical and psychological examinations or tests and that confidentiality is adequately protected. This category includes protocols that pose “no greater than minimal risk” according to federal regulations.”

This study does include patients who are currently acutely suicidal and/or recently hospitalized because of suicidality. By definition, these patients are inherently high-risk participants; however, the question to consider for this research is whether the study procedures are likely to make the participants more suicidal. We believe the answer is no. Past research found that many of the patient participants enjoyed providing their feedback during the interview sessions and having their opinion/perspective valued. Some also described that for the moments they were interacting with the research team, their mind was off their worries. Preliminary data from our non-randomized observational research has demonstrated that suicidal patients feel less distressed following contact with our research team and use of Jaspr. Our research to date has demonstrated a 30% reduction in overall self-report ratings of distress for suicidal ED patients engaged in our research. Given the minimal risk nature of this study, the likely causes of such adverse events are likely to be factors related to their ED experience (e.g., nicotine withdrawal while in ED, fear/anxiety about what to expect, restrained on gurney, etc.) that co-occur or overlap with their engagement in our research, particularly during their ED stay. Unique research factors may include one or more of the following: length of the assessment, or interrupted use of Jaspr to attend to medical providers' interventions.

#### **E. Age**

Participants under the age of 18 will be excluded from participating in the study as suicide interventions and assessments for adolescents and children differ significantly from those for adults. While it is, in theory, conceivable that a portion of our provider participants will include older adolescents between the ages of 18 and 21, it is expected that these individuals will all be adults over the age of 21.

#### **F. Total Number of Participants to be Enrolled**

Participants will be recruited from healthcare systems and hospital EDs nationwide. For the ED RCT (and ED pilot RCT), we will gather data from approximately 135 suicidal ED patients (no fewer than 90 patients) and their health care

providers in the ED. We will recruit approximately 20 suicidal ED patients from each project site. To reach our recruitment goals for the RCT, we expect to spend an average of eight days at each site, with capacity to increase our time at each if needed. For the Telehealth study, we will gather data from approximately 60 outpatients experiencing suicidality. Outpatient participants will be recruited from clinics represented in the Dialectical Behavioral Therapy (DBT) Clinics Consortium (including Portland DBT Institute, Tampa Bay Center for Cognitive Behavioral Therapy, DBT Institute of Michigan) and, if needed, through an online distribution list of providers serving suicidal patients (ZeroSuicide, AAS, and DBT listservs).

## 5. Study Design / Method / Procedures

### A. Summary of the Research Design

EBPI is partnering with several large healthcare systems to conduct this research to ensure that Jaspr meets the needs and workflow of multiple large healthcare systems and persons who seek ED services for their suicidal behavior. Research with participants will occur onsite or remotely (via telephone and computer). For the ED study, each project performance site will decide if they prefer EBPI researchers to conduct all study procedures at their site or if they prefer to engage a qualified researcher to conduct the research in conjunction with EBPI researchers. EBPI will develop and maintain all the research protocol and procedures to be followed by EBPI and all site researchers. If applicable, EBPI will provide training to the site researchers (virtually or in-person) in the ED study research protocol and procedures prior to commencing research at each site, including training in approaching potential participants without coercion and the informed consent process. Moreover, all individuals engaging in research will be required to complete training in protection of human subjects in research, HIPAA training, and Good Clinical Practices education. Course completion certificates will be kept up to date during the study and stored by EBPI in their records.

Formal screening and the informed consent process will be performed by the researchers prior to commencing participation. Informed consent procedures will be fully and thoroughly conducted by a researcher (e.g., orienting prospective participants to the study details, highlighting that they are under no obligation to participation in the study, and that a decision to decline participation will not affect their care, in the case of patients, or employment, in the case of providers) onsite or remotely.

#### ED Study

**Patient Participants:** Because the patient's medical treatment is of foremost importance and to accommodate the fluid, unpredictable environments in the ED and to work within their usual flow, the researchers will pause all research procedures whenever necessary to allow for the patient's medical care and resume should there be additional periods of waiting. Once enrollment is complete (i.e., consent is obtained), the researchers will request a release of information from the participant for information we would like to gather from a member of their care team after the patient's discharge. Specifically, we are interested in collecting data about the patient's length of stay, if physical or chemical restraints were used and if so for how long, their final discharge disposition (e.g., if the patient was admitted to inpatient, residential, or substance abuse treatment or discharged to home), and if the patient was admitted whether it was involuntary or voluntary. This data will be obtained orally by speaking with a member of the patient's care team; medical records will not be accessed by the researchers. Permission (or not) for this release of information will not impact the patient's participation in the study (i.e., if they decline to provide permission for this release, they may still participate in the study). If the patient agrees to provide permission for the researcher to collect this information, they will be asked to sign a release of information form.

The researcher will then conduct the baseline assessment and the researcher will randomize the patient to condition while the participant is completing baseline measures. The researcher will inform the patient of the condition they have

been assigned after they have completed the baseline assessment.

If the patient is assigned to the CAU condition, the researcher will conclude the session and tell the patient that they will return in two hours to complete the post treatment interview and online surveys. If the patient is assigned to the Jaspr condition, the researcher will walk the patient through a supplement consent form to provide further information about the app and obtain their electronic or paper/pencil signature. The researcher will orient the patient to the app on the study tablet, help them to set up their account, and let them know they may use Jaspr however they choose for up to two hours, not including breaks they may request or that may be needed in order to receive their standard medical care. The researcher will remain with the patient at all times while using Jaspr to answer any questions that the patient may have about Jaspr or the study; the researcher will not engage with the patient otherwise. After two hours of Jaspr use, the researcher will ask the patient to pause their use of Jaspr and conduct the post treatment interview and online surveys. If the patient indicates they are finished using Jaspr prior to the two hour timeframe, the researcher will conduct the post treatment interview and online surveys at that time. After the post treatment surveys are completed, researchers will orient the patient to installing the Jaspr-at-Home mobile app on their smartphone and ask them to use it however they see fit after being discharged. If the patient does not have access to their smartphone or if they prefer to install the app after they leave the ED, the researcher will provide email instructions for accessing and installing Jaspr-at-Home.

Patient participants will be asked to contact the researcher in the unlikely event that they are going to be discharged or transferred prior to completing the post treatment surveys so that the patient may complete the study procedures prior to leaving. Time spent completing the initial session (i.e., eligibility, consent, randomization, baseline, scheduling, and post assessment) is estimated to take approximately 2 – 4 hours depending on the number of breaks the patient is required or elects to take.

After the post-treatment interview and surveys are completed in the ED, the onsite researcher will explain the purpose of blinding researchers to participants' condition and then virtually introduce (e.g., via Zoom, FaceTime) the patient participant to the (blinded) EBPI research assistant who will be responsible for conducting the post-discharge follow-up assessments. This research assistant will remain blind to the patient's condition during this discussion and the 7-, 30-, and most of the 90-day follow up assessment time points. At the very end of the 90-day assessment, the research assistant will be asking condition-specific questions (e.g., usability questions about the patient's experience with the Jaspr app) and thus cannot be blind during this assessment time point. In an effort to ensure a warm hand-off from the ED-based researcher to the follow-up blinded assessor, the blinded research assistant will schedule the three follow up assessments and administer the Participant Information Form.

Because the site contact or their designee will determine sufficiently stable participants to refer to the research, we do not anticipate that participation in the study will lead to significant distress. However, the researchers will be attentive to changes in mood states and, if indicated, will check in verbally with the participant about whether they wish to continue. If a participant becomes more distressed during the meeting for whatever reason (e.g., due to length of waiting in the ED, an upsetting conversation with medical personnel, or some aspect of the research procedure), the researchers will again ask if they prefer to discontinue the study. We prefer not to automatically discontinue the study in cases where their distress is caused by an aspect of their ED experience for the reason that participation in the study may actually be helpful to them in distracting them from the actual cause of their upset. We will however inquire about their preference to discontinue. We will also inform the site contact or their designee and a member of the patient's care team that the patient appears more upset than at the start of the research procedure. In cases where the patient appears more distressed than they were at the start of the procedure and displays difficulty redirecting to research tasks, we will discontinue the study procedure and notify the site contact or their designee and a member of the patient's care team.

Follow up assessments will occur remotely via phone and internet 7-, 30-, and 90-days after baseline. At the pre-  
Evidence-Based Practice Institute | [name] | [contact] | [[contact]](mailto:[contact])

arranged time, the researcher will call the patient to conduct the study follow up assessment. The researcher will first send the patient a link to the online surveys via email and verbally remind the participant of their study ID. The researcher may also text the study ID to the patient if they prefer. The researcher will mute their phone and remain on the line as the patient completes the surveys. The researcher will unmute their phone and address any questions the patient may have as needed. Upon completion of the surveys, the researcher will then conduct the semi-structured interview.

The researcher will conclude the assessment by asking the patient to rate their level of stress, urge to self-harm, intent to kill self, intent to physically harm self using a 7-point Likert scale (based on [name] UWRAMP protocol). If the patient endorses a score of 5 or greater on urges to harm self or others or if a patient participant becomes distressed during or immediately after the follow up assessment, the researcher will do a warm hand off to Boys Town and inform the study PI immediately. Boys Town Hotline is staffed by a specialized team of crisis counselors trained in providing suicide risk assessments by telephone in accordance with the National Suicide Prevention Lifeline's Suicide Risk Assessment Standards. Boys Town Hotline will provide telephone crisis intervention services and will provide the research staff documentation, including information given during the call, the nature of the call, responses given, and other evaluative data elements, to the study PI within 24 hours. Boys Town will utilize their national internal database of service referrals to provide further action for the participant if deemed necessary. If the crisis counselor determines the participant's situation as life threatening, they will notify a senior counselor who will determine the level of assistance needed (i.e., if another party should be contacted, facilitation of contact with third party, and monitor the call while crisis counselor endeavors to remain actively engaged with the participant).

**Provider Participants:** The ED providers and other hospital staff of each participating site will be knowledgeable about the study. The researchers will provide further information as needed for providers to refer patients to the study. Interested provider participants will enroll in the study prior to referring potential patient participants. After enrollment is complete, the researcher will set up the provider's Jaspr account and provide a brief introduction to the app.

After their index patient is enrolled in the study, the researchers will inform the provider of their patient's study condition via the method preferred by the provider as indicated during their consent process (e.g., verbally in person, via page or text message; no identifying information will be included by text or other electronic communication). Providers will be asked to treat their enrolled patient participants utilizing either the care they typically provide or the care they typically provide supplemented with Jaspr, depending to which condition the patient is assigned (CAU or Jaspr, respectively). While providers are treating a patient participant assigned to the Jaspr condition, they will be asked to utilize the provider summary reports and other tools within Jaspr as they see best, guided by their clinical judgement. Once the disposition discharge report is available from the patient participant's use of Jaspr, the researcher will print it out and provide this report to the provider participant to use as they see fit. After their index patient has used Jaspr for up to two hours (not counting breaks) or received usual care for two hours, all providers will be asked to complete a brief post treatment interview. They may also choose to complete the survey on paper or online if they prefer. In the case of a patient participant having multiple providers (e.g., social worker), the researcher will gather feedback from the ED physician or main provider and then from the other providers who also treated the patient participant given these other providers also have enrolled in the study. Participation time for providers per patient is approximately 5 minutes including enrollment procedures.

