The focus of this summative evaluation is to evaluate Jaspr (N=120) and JAH (N=60) in clinical trials. The ED clinical trial compares Jaspr to Care-as-Usual (CAU) in EDs nationwide; the Telehealth clinical trial compares JAH to CAU + crisis safety plan. Patient participants meeting study criteria for the ED study will be randomly assigned to receive Jaspr (in addition to their usual care; n=60) or CAU only (the treatment that is standardly provided to suicidal patients in the ED; n=60). Patients participants in the ED study who are assigned to the Jaspr condition will receive access to JAH for use throughout the follow up period as they see fit. Outpatient participants meeting study criteria for the Telehealth study will be randomly assigned to receive JAH (in addition to their usual care; n=30) or CAU (in addition to crisis safety planning; n=30). We will also conduct a small (N=15) ED study pilot trial to make necessary adjustments to both study procedures and Jaspr before conducting the ED study RCT. The research procedures for the pilot and full RCT will be identical unless the research team identifies areas for improvement during the pilot to incorporate into the full RCT. All modifications will be submitted to IRB prior to implementation.

Patient participants in the ED study will be asked to complete study sessions (interview and online surveys) at four time points: at the time of ED admission, and at 7-days, 30-days, and 90-days after ED admission. Outpatient participants in the Telehealth study will be asked to complete study sessions at three time points: baseline, 30- and 90-days after the initial session. The initial session of the ED study will be conducted in-person in a private space provided by the organization/hospital (e.g., the patient’s room or another private environment); the initial session of the Telehealth study will be conducted remotely. Each follow up assessment will be conducted remotely consisting of a brief phone

interview and a set of surveys administered online.

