The ED study will also include provider participants who will be asked to complete a demographics survey and a brief interview about each of their index study patients after their intervention with the patient is complete. The brief interview will be administered in-person and assess the provider's feeling of preparedness for the assessment, the patient's degree of distress at the time of encounter, helpfulness of Jaspr's clinical support tool in discharge disposition determination, and risk assessment (if applicable).

ED study primary outcome variables include: suicidality (death by suicide, suicide attempts, suicidal ideation), ED/hospital admissions, discharge disposition, use of restraints while in ED (chemical, physical), intensity ratings of acute distress, self-efficacy in coping with distress, use of imminent distress intervention and coping skills, and helpfulness of their ED encounter. Jaspr condition-specific outcomes will be examined and reported descriptively. These include tools accessed during and after the ED visit, perceived usefulness and satisfaction of Jaspr brief intervention components, and usage of provider/patient apps and their features.

Telehealth study primary outcome variables include: suicidality (death by suicide, suicide attempts, suicidal ideation); Crisis-related healthcare utilization (ED visits, psychiatric hospitalization, calls to crisis line; crisis calls to therapist; Outpatient Satisfaction; Use of evidence-based interventions to reduce suicide risk (safety planning, lethal means management, behavioral skills). Secondary outcomes include: Reasons for living; Psychological distress (depression, anxiety, stress); Cognitions associated with suicide risk (hope, optimism, pessimism).

The primary hypotheses include:

1. Jaspr patients will report significantly greater decrease in suicidality and ED/hospital admissions than CAU patients from the initial session to follow-up assessments.
2. Jaspr patients will report significantly greater increases in self-efficacy in coping with acute distress, use of acute crisis tolerance skills, and perceived helpfulness of the care they receive compared to CAU patients.
3. Jaspr patients will report high levels of satisfaction with Jaspr.

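### Restraint use, a primary ED outcome, has no window starting at randomisation, so on the natural reading restraint that Jaspr could not have affected counts as an outcome

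*Combined protocol and SAP*

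**What the plan says.** Section 3 (Introduction) lists "use of restraints while in ED (chemical, physical" among the primary outcome variables of the ED study. The stated period is the ED stay; randomisation is not mentioned.

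Section 5.A (ED Study, Patient Participants) says how it is obtained. With a signed release, it is part of the "information we would like to gather from a member of their care team after the patient's discharge", alongside length of stay and final disposition. The item is "if physical or chemical restraints were used and if so for how long". On the source, the text says: "This data will be obtained orally by speaking with a member of the patient's care team; medical records will not be accessed by the researchers". A patient may decline the release and stay in the study.

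Randomisation happens during the visit, after screening and consent: "the researcher will randomize the patient to condition while the participant is completing baseline measures". Section 4.A requires that patients be "stable as deemed by ED medical personnel or other treatment provider" and excludes those who are "acutely psychotic, severely agitated".

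Nowhere do the documents give a post-randomisation window for restraint, a baseline restraint variable, or a sensitivity analysis for earlier restraint.

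**The concern.** An outcome in a randomised comparison should be able to respond to the treatment. Restraint that ended before allocation cannot. If it is counted, both arms carry events that are the same in expectation and say nothing about Jaspr.

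The analysis in section 5.B does not remove them. It relies on the Time X Condition interaction with baseline as the reference, but restraint is recorded once per stay and has no baseline value. Because charts are not consulted, timing that is not asked for in the conversation cannot be recovered afterwards.

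At stake is the estimate for a named primary outcome: a real reduction would look smaller than it is and would be harder to detect.

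**Working it through.** **The plan's own figures.** Section 5.B (Statistical Power Considerations) gives 24 patients, then 24 × 3.0 = 72 for the design effect, then 72 / (1 − 0.20) = 90 for attrition. The 24 is reproduced by a repeated-measures interaction test with f = 0.25, if one assumes four time points and a correlation of 0.5. These figures concern a medium Time X Condition effect. None is stated for restraint.

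**Inputs from the documents.** 60 per arm (section 3: "Jaspr (in addition to their usual care; n=60) or CAU only", with the same number in CAU); two-sided test at 0.05 (section 5.B).

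**Assumed inputs.** All restraint rates. Events before and after randomisation are first taken as independent. No design effect is applied.

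**Formulas.** Let p be the risk of restraint before randomisation (the same in both arms in expectation), and c and t the risks after randomisation in CAU and Jaspr.

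- Whole-stay risk: 1 − (1 − p)(1 − c) in CAU and 1 − (1 − p)(1 − t) in Jaspr.
- Whole-stay risk difference: (1 − p)(c − t).
- Whole-stay risk ratio: [p + (1 − p)t] / [p + (1 − p)c]. For t < c this rises towards 1 as p grows.

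**Results at 60 per arm** (two-proportion normal approximation):

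| After randomisation, CAU v Jaspr | p | Whole stay, CAU v Jaspr | Risk difference | Risk ratio | Power |
|---|---|---|---|---|---|
| 20% v 8% | 0 | 20.0% v 8.0% | 0.120 | 0.40 | 47% |
| 20% v 8% | 5% | 24.0% v 12.6% | 0.114 | 0.53 | 36% |
| 20% v 8% | 10% | 28.0% v 17.2% | 0.108 | 0.61 | 29% |
| 20% v 8% | 20% | 36.0% v 26.4% | 0.096 | 0.73 | 20% |
| 10% v 5% | 0 | 10.0% v 5.0% | 0.050 | 0.50 | 18% |
| 10% v 5% | 10% | 19.0% v 14.5% | 0.045 | 0.76 | 10% |

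For example, with p = 10%: 1 − 0.90 × 0.80 = 0.280 and 1 − 0.90 × 0.92 = 0.172; 0.172 / 0.280 = 0.61.

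**Without independence.** Fix the whole-stay CAU risk at 20% and let Jaspr halve only what arises after randomisation. If nothing arises before, the comparison is 20% v 10% (risk ratio 0.50, power 33%). If half arises before, it is 20% v 15% (0.10 + 0.10 × 0.5 = 0.15), with risk ratio 0.75 and power 11%.

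**Duration.** Earlier minutes add the same expected amount to both arms, so the difference in means is unchanged and only the variance grows. If earlier restraint adds as much variance as later restraint, the standard deviation rises by √2. Power for a standardised difference of 0.5 then falls from 78% to 49%.

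**The case against.** Several points on the other side stand.

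- **The window is inferred.** The text does not say that restraint before randomisation is included. The passage in section 5.A describes what the release covers, and the care-team form is not in the documents. Still, a period described as the ED stay, asked about after discharge with no start point, most naturally means the whole visit.
- **Clustering before enrolment is not shown.** A reader might infer from the stability requirement and the exclusion of severe agitation that most restraint comes before enrolment. The documents do not establish this. Section 4.D (Vulnerable Populations) names restraint among ED experiences that can overlap with research participation, and section 3 places the first session at ED admission, which suggests a short earlier interval. Neither makes that interval empty.
- **The comparison stays valid.** A reader might infer bias between arms. Randomisation balances earlier restraint in expectation, and chance imbalance is already covered by the type I error rate. With 10% restrained beforehand in each arm, the chance that the arms differ by five or more such patients is about 17%. That is noise a covariate could absorb, not an added bias.
- **The power gain is limited.** In the lead illustration power is only 47% with the right window, and patients who decline the release lower it further. None of the three primary hypotheses names restraint, and the sample size was not set for it. The attenuated estimate remains whatever the power.

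**Conclusion.** The point holds: a listed primary outcome lacks a window tied to randomisation, and followed as written it would take in events that Jaspr could not affect. The consequences are an attenuated risk difference and risk ratio for any use, and extra variance for duration.

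The direction for any use follows for every p above zero when Jaspr reduces restraint and the events are independent. The size cannot be computed from the documents. In the lead illustration, a risk ratio of 0.40 becomes 0.61 with 10% restrained beforehand and 0.73 with 20%, and power falls from 47% to 29% and 20%.

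It would go too far to say that every treatment effect on restraint is diluted: the absolute difference in mean duration is not.

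**What to change.** 1. Define the outcome as restraint after randomisation, both any use and duration, and state how an episode in progress at randomisation is counted.
2. Record the clock time of randomisation.
3. Once the release is signed and before allocation, ask the care team whether restraint has already been used in this visit and for how long. Use the answer as a baseline covariate.
4. In the conversation after discharge, ask only about restraint since the recorded time of randomisation.

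The earlier period should be asked about at enrolment, not in the same conversation after discharge. Section 5.A (Provider Participants) has providers told their patient's condition, so staff who may know the allocation would otherwise decide from memory what came before it. That could replace noise common to both arms with misclassification that differs between them. The release is already requested before the baseline assessment, so the question fits the existing sequence.

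The cost is one short extra question at enrolment. Some recall error about timing will remain in the post-discharge report from staff who may know the allocation. The change will not by itself make restraint an adequately powered outcome.
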